SUPPLEMENTAL DATA ANALYSIS PLAN

Project Title: Hybrid Effectiveness-Implementation Trial for ART Adherence and Substance Use in HIV Care in South Africa

Principal Investigator: [name]

Grant: K23DA041901

Version Date: 9 December 2019

DATA ANALYTIC PLAN

Implementation Outcomes

Quantitative. Descriptive statistics will be generated to evaluate implementation outcomes. Total scores from the acceptability and feasibility subscales of the AMHR pragmatic implementation assessment will be created; these scores, alongside data obtained on provider fidelity to the intervention and patient participation and retention will first be evaluated descriptively. The means and standard deviation of provider fidelity at each session will be calculated. The percentage of patients participating and retained in the intervention will be described. These implementation outcomes will be compared with other similar pilot studies and used as pilot data for the subsequent R01 proposal from this K23 award.

Qualitative. Data from individual interviews to assess implementation outcomes will be analyzed iteratively and follow descriptive qualitative thematic analysis. Guided by RE-AIM and Proctor's model for defining implementation outcomes, initial concepts related to the central research questions listed will be identified based on the semi-structured interview guide. Concepts will be used to develop a codebook consisting of a label, a definition, and illustrative quotes from the data. All transcripts will be coded independently by two research assistants. Final themes will be agreed upon and inter-rater reliability of coding assessed. Following recommendations of mixed methods designs, we will integrate findings from the qualitative and quantitative methods using a convergent QUANT + qual mixed methods design to assess implementation outcomes. Specifically, themes from the qualitative interviews will be compared with the quantitative descriptive data on feasibility and acceptability, assessing for both convergence and divergence.

Effectiveness Outcomes

Quantitative. Quantitative longitudinal analysis will examine changes in ART nonadherence, substance use, and viral load from baseline to post-treatment between the conditions. If appropriate after examining descriptive data, normality, and assumptions, T-tests may be used to compare continuous variables (e.g., age, ART nonadherence) and Fisher's exact test may be used to compare categorical variables (e.g., gender, urinalysis). If the appropriate statistical assumptions are met after examining distributions of main outcome variables, longitudinal data analysis using generalized linear mixed models (GLMM) will be used to compare the two study arms over time. This approach increases power by including all available data points. We will adjust the analyses for relevant baseline demographic characteristics (e.g., gender, age) for each analysis, and clinical differences that exist between the two treatment arms. Intent-to-treat analyses will be utilized, where all individuals will be analyzed according to the condition to which they were randomized.

The published version of our protocol paper that outlines this data analytic plan can be found online at:

Magidson, J. F., [name], J. A., [name], B., Belus, J. M., Regenauer, K. S., [name], L. S., ... & [name], S. A. (2020). Project Khanya: A randomized, hybrid effectiveness-implementation trial of a peer-delivered behavioral intervention for ART adherence and substance use in Cape Town, South Africa. *Implementation Science Communications*, 1, 23. doi: [10.1186/s43058-020-00004-w](https://doi.org/10.1186/s43058-020-00004-w)

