Consent procedures. Potentially eligible patients identified by their HIV primary care clinic as either (a) having a VL > 400 copies/mL, (b) being on second-line treatment, (c) having been reinitiated on first-line treatment within the past three months, or (d) having a pharmacy non-refill at least once in the past three months, will be screened for substance use by the research assistant or field worker using the WHO-ASSIST. If preliminary criteria are met, eligible patients will be briefed on study procedures; if interested, they will provide informed consent. Before signing the consent form, participants will receive a comprehensive and interactive explanation of the study by staff. Study personnel will receive training regarding procedures required to obtain informed consent, and training and supervision will be completed on an ongoing basis to continually reinforce such procedures. All study personnel will also be appropriately trained in the ethical conduct of human subjects research and will be required to recertify annually.

The consent form will include all the study participations, information about potential risks and benefits of participation, and information regarding whom they can contact for further questions. It also will state that participation is voluntary, that participants can refuse to answer any question, that participants can withdraw from the study at any time, and that study participation is in no way related to their care received at the clinic. All participant questions will be answered before they are asked to sign the consent form. Additionally, patients who provide informed consent will also be invited to sign a release of information to allow access to their medical record for current ART regimen, time on ART, viral load, and CD4 count (for up to two years after study entry for study monitoring purposes). Participants will be provided with a copy of the consent form for their own records.

All procedures and protocols will be approved by the University of Cape Town HREC and the US-based site (University of Maryland) before study initiation. Study staff will review all informed consents within one week of their completion.

[figure not shown]

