Description: Wisepill is a real-time, wireless, electronic adherence monitoring device used to assess ART adherence in real time.^{54,55} Wisepill uses cell phone technology to transmit a real-time signal to a web server when the pill box is opened. Participants do not need to come into the clinic for the study to obtain readings. A dose will be considered 'taken' if the box is opened \pm 2 hours from the prescribed time.⁵⁴ The study will also use the recommended methods for Wisepill data collection and analysis, which are to adjust for technical malfunctions, loss of signal, and self-reported pocket doses.^{54,55} Participants in both conditions will be given a Wisepill box at the baseline visit, and the 2-week period between baseline and randomization will serve as the baseline adherence measure. We will calculate % doses missed vs. prescribed. Participants will use the Wisepill box during the first three months of the study (which maps onto the intervention period), and return the device at their post-treatment assessment.

Time Frame: Approximately 10-weeks post-randomization (post-intervention assessment)

B. Substance Use

a. **Title:** Biological measure of substance use (alcohol, drugs)

Description: Biological measure of substance use. Drug use will be assessed using urinalysis (rapid detect 6-panel urine tests (cocaine, marijuana, amphetamines, opiates, phencyclidine, alcohol).

Time Frame: Approximately 10-weeks post-randomization (post-treatment assessment, primary outcome) and 22-weeks post-randomization (6-month follow-up assessment, secondary outcome)

b. **Title:** WHO-ASSIST

Description: Score on the Alcohol, Smoking, and Substance Involvement Screening Test (WHO-ASSIST). The WHO-ASSIST was developed for the World Health Organization (WHO), and is used to detect and manage substance use and related problems in primary and general medical care settings. The test screens for alcohol, cannabis, cocaine, opiates, amphetamines, hallucinogens, and other drug-related problems in primary care and has been validated in South Africa. It categorizes individuals into low (0-3 for illicit drug use), moderate (4-26 for illicit drug use), or high risk (>26 for illicit drug use) for substance use related problems.

Time Frame: Approximately 10-weeks post-randomization (post-treatment assessment: primary outcome) and 22-weeks post-randomization (6-month follow-up assessment: secondary outcome)

C. Feasibility & Acceptability of Intervention

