1. CD4 count and Viral Load: CD4 count and viral load will be extracted from participants' medical record at each major visit. If results are not available within 3 months of the baseline assessment and 30 days of the follow-up assessments (post-treatment assessment and 6-month follow-up assessment), participants will be invited to undergo a blood draw. These procedures will not add any cost to the patient. CD4 count will be used as a measure of immune function and disease progression. Viral load will be used as a biological indicator of ART adherence. Viral load will also be used to document the percentage of the sample with virological suppression (measured dichotomously at < 400 copies/mL).
2. Dried Blood Spot (DBS): We will be collecting and storing dried blood spots. Analysis by DBS will allow for a gross confirmation that at least some recent ART is present in the system.⁷⁹ This biological confirmation will be used as verification of Wisepill data. One vial of blood for DBS will be taken at each major assessment. In addition to adherence, we are storing DBS for future biomarkers in our freezer. We will ship and then destroy samples before five years after the study is completed.
3. Urinalysis. Urinalysis will be used as a biological indicator of alcohol and drug use. Urinalysis will be conducted at all major assessments (baseline, post-treatment assessment, 6-months follow-up assessment) and at intervention participants' third session (halfway through the intervention) by a trained research assistant using rapid detect urine tests. Control participants will also be asked to come into the clinic for urinalysis between their baseline and post-treatment assessment (approximately 5-weeks post-randomization). These urine tests detect cocaine, marijuana, amphetamines, opiates, phencyclidine and alcohol, and give dichotomous results. Since there is potential stigma related to substance use, and participants may falsely believe that ART will be withheld in the context of use,⁶⁶ study procedures include dialogue with the participant to ensuring anonymity of the results.

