Statistical tests (such as t-test and Wilcoxon rank sum test) will be used to compare continuous study outcomes (e.g., ART nonadherence) between the two arms at baseline. For comparison of categorical outcomes (e.g., urinalysis), Fisher's exact test will be used. Longitudinal data analysis using generalized linear mixed models (GLMM) will be used to compare the study endpoints (ART nonadherence, substance use, viral load at 6 months) between the two arms after adjusting for the effect of other covariates (e.g., gender, age). This approach increases power by including all available data points. Intent-to-treat will be utilized, where all individuals will be analyzed according to the condition that they were randomized. Effect size estimates will be generated to provide estimates to power for a larger future grant application.

Table 1. Levels of power based on varying differences in adherence detected.

Predicted Avg Adherence in Control Group	Predicted Avg Adherence in Tx Group	Difference in Avg Adherence	SD of Estimated Adherence	Power
0.55	0.85	0.30	0.25	0.99
0.55	0.80	0.25	0.25	0.97
0.55	0.75	0.20	0.25	0.88
0.55	0.73	0.18	0.25	0.80
0.55	0.70	0.15	0.25	0.64
0.55	0.65	0.10	0.25	0.34

ETHICAL CONSIDERATIONS AND RISKS TO THE SUBJECTS

A. Risks to participants.

Human subjects involvement and characteristics.

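### The SAP lets observed arm differences choose the clinical covariates, and neither document says how each outcome's pre-randomization value enters the mixed model

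*SAP*

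**What the plan says.** **Covariates.** The SAP (Effectiveness Outcomes, Quantitative) will "adjust the analyses for relevant baseline demographic characteristics (e.g., gender, age) for each analysis, and clinical differences that exist between the two treatment arms". It names no clinical variable, test, significance level or size of difference. The protocol's data analytic plan (Methods, section E) compares the endpoints "between the two arms after adjusting for the effect of other covariates (e.g., gender, age"), again only by example. Protocol section D treats the non-primary measures generally as possible covariates, and its SOCRATES item gives that scale particular weight as one. Neither analysis section turns this into a set.

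**Use of baseline.** The SAP states: "Quantitative longitudinal analysis will examine changes in ART nonadherence, substance use, and viral load from baseline to post-treatment between the conditions". If assumptions are met, "generalized linear mixed models (GLMM) will be used to compare the two study arms over time". Neither document says whether the baseline value is a covariate, a response row, a mean held common to the arms, or part of a change score.

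**What is collected before randomization.** For Wisepill, "the 2-week period between baseline and randomization will serve as the baseline adherence measure" (section D, HIV Medication Adherence). "Urinalysis will be conducted at all major assessments (baseline, post-treatment assessment, 6-months follow-up assessment") is in section D, Other Collected Data. Potentially eligible patients "will be screened for substance use by the research assistant or field worker using the WHO-ASSIST" (section C, Consent procedures); the table of measures at major assessments marks the ASSIST at screening and not at baseline. Viral load is taken from records or a blood draw at baseline.

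**Use of the result.** Protocol section E: "Effect size estimates will be generated to provide estimates to power for a larger future grant application".

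**The concern.** Chance imbalance between arms of 30 is expected, and it says little about whether a variable predicts the outcome. A rule driven by imbalance therefore tends to leave out a strong predictor when the arms happen to match on it. It also cannot be applied reproducibly when the threshold is unwritten: two analysts following the SAP could fit different models to the same data.

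The outcome's own earlier value is usually the covariate most worth having. Whether and how it is used decides the width of the interval, and the effect sizes are meant to power a later study.

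**Working it through.** **Inputs.** Protocol section E: difference 0.18, SD 0.25, 30 per arm, two-sided alpha 0.05. The documents give no baseline/post correlation (rho), so 0.3 / 0.5 / 0.7 is assumed. Also assumed: one post measure, complete normal data, and equal baseline and post SD.

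**1. The plan's own figure.** SE = 0.25 × √(2/30) = 0.0645, and 0.18/0.0645 = 2.79. Power is 79.6% by the normal approximation and 78.3% by the noncentral t, against 80% stated. All six rows of the power table reproduce within 2 points. This is an unadjusted comparison of two means.

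**2. Prespecified baseline adjustment.** Residual SD = 0.25 × √(1 − rho²) = 0.238 / 0.217 / 0.179, so SE = 0.0616 / 0.0559 / 0.0461. Noncentral-t power (57 df) is 82 / 89 / 97%. Simulation gives about 81 / 88 / 97%.

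**3. Two alternative readings of the plan.** They cannot both apply to the same outcome.

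*Reading A: post values, with the outcome's baseline added only if the arms differ on it.* This is nearer the protocol's wording. It was simulated with 40,000 trials per cell.

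*Reading B: baseline as a response row, with arm, time, arm-by-time and free baseline means.* This is nearer the SAP's wording about change. On one simulated complete data set, a random-intercept model of this form gave the same estimate and SE as the difference in mean change. SD = 0.25 × √(2(1 − rho)) = 0.296 / 0.250 / 0.194, so SE = 0.0764 / 0.0645 / 0.0500.

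| Analysis | Power at rho 0.3 / 0.5 / 0.7 | 95% CI half-width, points |
|---|---|---|
| Prespecified baseline adjustment | 82 / 89 / 97% | 12.3 / 11.2 / 9.2 |
| A, threshold p<0.05 | 78 / 79 / 80% | not computed |
| A, threshold p<0.20 | 79 / 81 / 84% | not computed |
| B, free baseline means | 64 / 78 / 94% | 15.3 / 12.9 / 10.0 |

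**4. Precision under A.** Of the variance reduction that full adjustment gives, the rule recovers about 24–27% at p<0.05 and 63–66% at p<0.20.

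**5. Effect of the unwritten threshold under A.** A baseline difference at exactly p=0.05 is 12.9 points, so adjusting or not moves the estimate by rho × 12.9 = 3.9 / 6.5 / 9.0 points. At p=0.20 it is 8.4 points, a move of 2.5 / 4.2 / 5.9. In the 15% of trials that fall between these thresholds, the mean move is 3.0 / 5.0 / 7.1 points. The side of p=0.05 changes in 14 / 22 / 32% of those trials, or about 2 / 3 / 5% of all trials.

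**6. Cost under B.** The variance ratio to baseline adjustment is 2(1 − rho)/(1 − rho²) = 2/(1 + rho) = 1.54 / 1.33 / 1.18. Matching adjustment at 30 per arm would take about 46 / 40 / 35 per arm. Holding the baseline mean common to the arms would remove most of this loss.

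**7. Other clinical variables.** Under B the outcome's baseline is already in the model, so the rule acts only on other measures. With 10 independent candidates (assumed), the chance that at least one is selected is 1 − 0.95¹⁰ = 40% at p<0.05 and 1 − 0.80¹⁰ = 89% at p<0.20. In a separate simulation of post values under no effect, with each candidate correlated 0.2 with the outcome (assumed), the spread of estimates across no adjustment and thresholds of 0.05, 0.10 and 0.20 averaged 3.4 points.

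**8. Type I error under A.** It is 4.7 / 4.3 / 3.5% at p<0.05 and 4.5 / 3.8 / 2.5% at p<0.20.

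**9. Urinalysis, illustration only.** Assume 60% positive at baseline and in control, 25% positive with intervention, and phi 0.2 / 0.3 / 0.4. A test stratified by baseline result has 81 / 83 / 86% power; a marginal arm-by-time log-odds contrast has 57 / 63 / 70%. Prevalence, phi and effect are all assumed, and no logistic GLMM was fitted.

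**The case against.** The strongest reply is that baseline is plainly meant to be used: the SAP speaks of change and of comparison over time. Free baseline means are only one way to fit that, and a common mean is equally open. At rho 0.5, change-by-arm matches the planned power, and at 0.7 it exceeds it. This stands: Reading B loses against the plan's own figure only at low correlation, and the correlation is assumed. It does not close the gap, because baseline adjustment is more precise at all three values and the text does not choose.

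Other points stand in part. The SAP cites a published protocol paper that may give the detail; it was not seen, so the gap is shown for these two documents only. The plan means to use all available data points, and Wisepill is continuous, so one post measure is a simplification. The trial is a pilot, but its estimates are intended for a later power calculation.

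Three stronger inferences are tempting and not supported:

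- *The rule inflates false positives.* A fixed threshold makes the test conservative (step 8). In the step 7 simulation, taking the smallest p-value across the four rules gave 6.6%, but nothing in the documents says the rule would be chosen that way.
- *The 80% power is wrong.* It reproduces.
- *The rule wastes nearly all the available precision.* It recovers about a quarter to two thirds of the variance reduction, depending on the threshold.

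**Conclusion.** The point holds as a gap in specification with a better method available at no cost. It should be fixed; it does not invalidate the design. The SAP selects clinical covariates from observed arm differences without a list or threshold, and neither document gives the role of the outcome's pre-randomization value.

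Compared with prespecified baseline adjustment, Reading A gives up about 4 / 10 / 17 points of power at p<0.05 (82−78, 89−79, 97−80) and 3 / 8 / 13 at p<0.20. Reading B with free means gives up about 18 / 11 / 3. Near the threshold under A, the estimate shifts by a mean 3 / 5 / 7 points against an 18-point target.

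These sizes rest on the assumed correlations, one post measure and complete normal data with equal SDs. If the two-week Wisepill baseline were noisier (SD 0.30, assumed), Reading B would fall to 55 / 69 / 88%, while adjustment at a given rho would be unaffected. That the text leaves the model open does not depend on any of these figures.

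**What to change.** In the SAP's effectiveness section, with matching wording in protocol section E, replace the clause that ties clinical covariates to arm differences with a set that does not depend on observed imbalance:

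- **Covariates:** age, gender and the outcome's own pre-randomization value. Name that value for each outcome: two-week Wisepill nonadherence; the screening score of the ASSIST scale analysed; the baseline result of the urinalysis endpoint analysed; baseline viral load for the exploratory outcome.
- **How baseline enters:** either as a covariate or through a GLMM with a common baseline mean across arms, but not both.
- **Contrast:** between arms at post-treatment as primary and, for urinalysis and ASSIST, at the 6-month follow-up as secondary, as section D sets out.
- **Missing baseline, if it is a covariate:** replace it by the mean of both arms pooled, so that no randomized participant is lost.
- **Anything further, such as SOCRATES:** name it in advance or keep it to labelled sensitivity analyses.
- **Baseline comparisons of the arms:** keep them as description and do not use them to choose covariates.

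The cost is one replaced clause and a short list in the SAP, with matching protocol wording. No new data, visits or participants are needed.
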